## Phase 1: Focus Groups

**Setting:** In order to obtain samples that are diverse (e.g., rural vs. urban, race/ethnicity, CBOC utilization) and improve VHA generalizability, focus groups will be held at the Greater Los Angeles (GLA) and the Iowa City (IC) VA Health Care Systems. The focus groups will be held in conference rooms at the respective VAs so that the groups are readily accessible and in a familiar environment.

**Participants:** Potential focus group participants will be identified through VA administrative databases at the respective medical centers. Focus group participants will be delimited to OEF/OIF/OND Reserve and National Guard (RNG) servicewomen with PTSD who have returned from deployment in Iraq or Afghanistan within the prior 24 months. Focus groups will be composed of women who have had at least one VA encounter within the preceding 18 months. Participation inclusion, described in the informed consent, will be limited to those with no disabilities that would impair their ability to provide consent and participate in the groups. Following chart review and consultation with evidence-based coordinators at each VA site, three focus groups with RNG women will be held for each specialty care group (Primary Care and specialty mental healthcare [MH]) according to EBT participation: 1) current or completed EBP, 2) EBP drop out, 3) never participated in EBP. Two VA sites (Greater Los Angeles and Iowa City) will be used, for a total of 12 focus groups (2x3x2). These data will be used to modify our current web-based tailored educational interface with modules specific to VA MH and PTSD/EBT perceptions and post-intervention satisfaction survey questions. Prior to implementation, the modified web-based interface will be pilot tested in a sample of 20 OEF/OIF/OND RNG women within two years post-deployment to Iraq or Afghanistan and within our study catchment areas (per Defense Manpower Data Center (DMDC) data) regardless of VA enrollment.

**Feasibility:** We verified sufficient participant availability for Phase 1 using administrative data (2011) at the IC VA using these eligibility criteria. We found that more RNG women with PTSD are seeking care in mental health (n=161) and have a greater range of visits than those seen in primary care (n=82). The GLA VA has an even larger women Veteran population.

**Focus Group Process:** Following IRB approval, participants will be recruited by US postal mail with a goal of 6-8 participants in each group. In order to participate they must be willing to be audio-recorded in the focus groups after being informed about the ways that their personal identities are not associated with the audiotapes and the strict security protocols that are followed to maintain confidentiality and data security. The population of Veterans meeting inclusion criteria is of sufficient size at each center that we do not anticipate recruitment difficulties. However, we will have alternative options such as semi-structured interviews or recruitment follow-up with a telephone protocol or recruitment by clinician referral. The 1.5 hour focus group sessions will be led in Los Angeles by [name], a qualitative expert, and [name], who is well experienced in performing

focus groups with RNG servicewomen. Participants will be reimbursed \$30.00 and refreshments will be provided. Women who contact the research coordinator to affirm focus group participation will receive an additional \$10.00. A protocol will be in place to address any mental health emergency or safety issues that may arise, but noting that this research team has experienced no adverse outcomes from prior focus groups with RNG servicewomen post-deployment.

[figure not shown]
**Qualitative Analysis:** The Aday and Andersen (Aday & Andersen, 1974) framework for assessing equity in access to health care will be a guide to the key domains that will be queried in the Phase 1 focus groups with regard to barriers and facilitators to VA mental health care and, moreover, EBP. Our initial analytic approach to the focus group data will use the constant comparison method, whereby we use open coding to identify salient issues and concerns raised by the participants across all of the groups. These open codes will be examined by the investigators in order to develop themes that pertain to the majority of focus group participants, with a focus on addressing the specific aims of the study (rather than all emergent themes). These themes will also be analyzed for their potential "fit" with the Aday and Andersen model, i.e., their relevance to the concepts of predisposing, enabling, and need characteristics. Assuming that there will be some degree of fit between emergent themes and conceptual domains, each conceptual domain will be summarized with reference to its applicability to refinements to the intervention as well as overall implementation processes. Focus groups will be digitally recorded and the Iowa City CADRE Qualitative Team will complete verbatim transcription. ATLAS.ti, a qualitative data analysis software program, will be used to assist this process. A codebook will be developed initially by the focus group co-facilitators with subsequent co-investigator independent coding of manuscripts from each of the focus groups specific to EBP participation (current or completed, never used, drop-out) and ultimately team consensus of codebook themes.

**Aim # 2:** To evaluate the participants' perceptions of and satisfaction with the revised web-based interface and to evaluate and test differences in VHA initiation and use for those who screen positive for PTSD by randomly assigned route: 1) Study concierge nurse case manager (NCM) or 2) existing outreach.

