
**Specific Aim #1: Using focus groups, identify VA enrolled OEF/OIF/OND RNG female war Veterans' perceptions, preferences and identified barriers and facilitators to accessing VA MH services and EBP (including cognitive processing therapies and prolonged exposure therapy) for PTSD.**

Hypothesis 1.a: OEF/OIF/OND RNG servicewomen with PTSD who differ in factors associated with access to care based on Aday and Andersen's (1974) model will identify different barriers and facilitators to VHA services for PTSD including EBP.

Hypothesis 1.b: With improved understanding of the consumer's perceptions of, or experiences with VA mental health care for PTSD and EBP, we can further tailor our existing web-based educational interface to better address the gap between PTSD care need and EBP access.

**Specific Aim # 2: To evaluate the participants' perceptions of and satisfaction with the revised web-based interface and to evaluate and test differences in VHA initiation and use for those who screen positive for PTSD by randomly assigned route: 1) Study concierge nurse case manager (NCM) or 2) existing outreach.**

Hypothesis 2.a: Web-based interface is a successful way to improve Veterans' post-deployment health education and VA access as demonstrated by web-intervention satisfaction survey and subsequent enrollment.

Hypothesis 2.b: Use of a nurse case manager to promote shared decision-making regarding PTSD services and EBPs will result in increased use of MH care and initiation of EBP for PTSD compared to outreach counselors.

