## **Conceptual Framework:**

Health disparities are “differences in the incidence, prevalence, mortality, and burden of disease and other adverse health conditions that exist among specific population groups in the United States” (NIH, 2002). Disparities in health attributed to harmful health exposures (e.g., combat or rape in military) or to factors related to limited access to health care (e.g., barriers to care while deployed or VA access) are considered inequities (Peters & Evans, 2001). Although racial/ethnic minorities and low-income groups have traditionally been the focus of health disparities research, we propose that military women, as VA treatment minorities, deserve this consideration. The identification and elimination of health disparities associated with female Veterans with PTSD is important because they are avoidable, unfair, and can affect our entire society (Woodward & Kawachi, 2000). The two-year costs of major depression and PTSD (including treatment costs, lost productivity and costs associated with suicide) for those deployed to OIF/OEF on June 30, 2008, were simulated to be close to \$925 million. If Veterans suffering from the disorders were all treated with evidence based treatment, policy simulations suggest that the savings generated would be \$138 million (Kilmer et al., 2011). We will use Aday and Andersen’s (Aday & Andersen, 1974) framework for assessing equity in access to health care. Aday and Andersen identified three groups of factors that affect service use: predisposing, enabling, and need characteristics. This framework will be a guide to the key domains that will be queried in the Phase 1 focus groups with regard to barriers and facilitators to mental health care and, moreover, VA evidence-based psychotherapy. Specific factors that affect service use include: *predisposing* (e.g., military rank, number of deployments), *enabling* (e.g., age, insurance, employment, rurality, VA care sites- primary care, MH, community-based outpatient clinic (CBOC)) and *need* (e.g., medical and mental health co-morbidities) characteristics.

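### The majority-theme rule in the focus-group analysis is not reconciled with Hypothesis 1.a or the stratified design, and can screen out subgroup-specific barriers

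*Combined protocol and SAP*

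**What the plan says.** All references are to the combined protocol and SAP.

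- **Hypothesis (1.0 Specific Aims, Hypothesis 1.a).** The hypothesis concerns women with PTSD "who differ in factors associated with access to care based on Aday and Andersen's (1974) model". Its prediction is that such women "will identify different barriers and facilitators to VHA services for PTSD including EBP".
- **Factors (2.0 Background, Conceptual Framework).** The model has predisposing, enabling and need factors. The enabling examples are "age, insurance, employment, rurality, VA care sites- primary care, MH, community-based outpatient clinic (CBOC"). EBP participation is not among the examples.
- **Design (4.0, Phase 1: Focus Groups, Participants).** Within each of two care settings (primary care and specialty mental health), separate groups are held by EBP participation: "1) current or completed EBP, 2) EBP drop out, 3) never participated in EBP". This is done at two sites, "for a total of 12 focus groups (2x3x2"). The recruitment goal is 6-8 women per group.
- **Analysis (4.0, Phase 1, Qualitative Analysis).** The initial approach is constant comparison, with "open coding to identify salient issues and concerns raised by the participants across all of the groups". From these codes the investigators "develop themes that pertain to the majority of focus group participants". The same sentence then narrows the work to what serves the aims: "with a focus on addressing the specific aims of the study (rather than all emergent themes"). The themes are then examined for fit with the Aday-Andersen model. A codebook is started by the group co-facilitators, co-investigators independently code the transcripts of the EBP-specific groups, and the team finally agrees the codebook themes.

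**The concern.** The hypothesis is about difference: women in different circumstances should report different obstacles. The groups are kept apart by EBP history, care setting and site, which makes such contrasts possible. The one stated criterion for a theme points the other way, because it favours what most participants share. A barrier felt strongly in one subgroup and absent elsewhere supports Hypothesis 1.a most directly, and it is also the kind least likely to meet a pooled majority.

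The focus-group results are used later. They modify the web modules (Phase 1, Participants) and supply the checklist of barriers and facilitators in the web survey (Phase 2 Intervention Process). The checklist is repeated after the web education, and the nurse case manager works from the items a participant has ticked. A barrier that never reaches the checklist cannot be ticked or prompt that discussion.

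**Working it through.** No power or sample-size formula applies to this phase, so the check is a count.

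**Inputs.** 2 care settings, 3 EBP strata, 2 sites and 6-8 women per group, all from Phase 1: Focus Groups. The denominator of the majority is taken as all participants. This is an assumption: the plan pools the codes over all groups but does not state the denominator.

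**The plan's own figure.** 2 x 3 x 2 = 12 groups, which reproduces the stated total.

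**One EBP stratum.** Each stratum has 2 settings x 2 sites = 4 groups. With equal groups of size m, its share is 4m/12m = 33.3%. A majority of N women is N/2 + 1 when N is even.

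| Group size | All women | One EBP stratum | Majority of all | Shortfall if the stratum is unanimous | Shortfall as share of other two strata |
|---|---|---|---|---|---|
| 6 | 72 | 24 | 37 | 13 | 13/48 = 27.1% |
| 7 | 84 | 28 | 43 | 15 | 15/56 = 26.8% |
| 8 | 96 | 32 | 49 | 17 | 17/64 = 26.6% |

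A unanimous stratum would therefore also need about 27% of the women outside it.

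**Unequal group sizes within 6-8.** The largest possible share for one stratum is 4x8/(4x8 + 8x6) = 32/80 = 40.0%. The smallest is 4x6/(4x6 + 8x8) = 24/88 = 27.3%. No allocation within the planned range reaches a majority.

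**One care setting (or one site).** Each has 6 of the 12 groups, so 50% with equal sizes, one woman short of a majority. With unequal sizes the range is 36/(36 + 48) = 42.9% to 48/(48 + 36) = 57.1%. Whether a setting-specific barrier qualifies then depends on attendance.

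**Would a majority within each stratum be enough?** The threshold would be 13 of 24, 15 of 28 or 17 of 32, about 18% of all participants (13/72, 15/84, 17/96). A barrier named by 12 of 24 women who dropped out of EBP would still be lost.

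**Search for an offsetting step.** The Qualitative Analysis contains no sentence that keeps minority or subgroup themes, and none that compares themes between EBP strata, care settings or Aday-Andersen subgroups. The model is used to judge the fit of themes and to summarise each domain. The coding of EBP-specific transcripts ends in team consensus, with no statement of what happens to content found in one stratum only.

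**The case against.** The strongest reply is that this reads a loose qualitative phrase as a counting rule. Several parts of it stand, and they rule out stronger conclusions that a reader might draw.

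- *That the rule removes stratum-specific barriers outright.* Not supported. It belongs to an initial approach, gives no count or exclusion step, and is followed by coding of the EBP-specific groups, which could bring such content back. The contrast drawn in the same sentence is with themes outside the aims, and Hypothesis 1.a is within them.
- *That the codebook is already filtered by the majority rule.* Not stated. The codebook is begun by the co-facilitators, and its themes are agreed only after the stratum-specific coding.
- *That Hypothesis 1.a is a hypothesis about EBP strata.* It is framed on Aday-Andersen factors. EBP status is how groups are formed; it is not a listed factor. Care site is listed, so the conflict with the hypothesis can be shown from care setting alone.
- *That the web modules and checklist will contain only majority themes.* No text limits them in this way. The loss downstream is a possibility, not a stated consequence.

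It is also fair that a broad theme may pertain to most women while its content differs by subgroup; the 33% figure does not exclude this. However, the reply supplies no retention or comparison rule. Even on the most generous reading, the plan states a criterion that favours shared themes and no step by which Hypothesis 1.a would be examined.

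**Conclusion.** The concern holds in a limited form. The majority criterion works against the plan's own hypothesis and makes poor use of its stratified groups, and nothing written offsets it. Read literally, it cannot admit a barrier confined to one EBP stratum (33% of participants, 27% to 40% over the planned group sizes). It does not admit one confined to a single care setting when groups are equal (50%; 43% to 57% otherwise).

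This rests on three assumptions: the majority is taken over all participants, group sizes stay within 6-8, and a theme is counted at the level of the specific barrier. How much subgroup content would actually be lost cannot be determined, because the later EBP-specific coding may recover some of it. No randomised comparison or power figure depends on this point. It should still be corrected before coding begins, since it bears on whether Hypothesis 1.a can be addressed and may affect what enters the web interface.

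**What to change.** In the Qualitative Analysis, replace the majority criterion with the following:

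1. Develop and retain aim-relevant themes within each EBP stratum and each care setting, and within other Aday-Andersen subgroups (such as rurality or rank) where the data allow.
2. Keep subgroup-specific themes without a pooled headcount threshold. A within-stratum majority should not take its place, because it would still drop minority barriers.
3. Report a theme-by-subgroup matrix, and compare subgroups from it for Hypothesis 1.a.
4. State that subgroup-specific barriers are carried into the web modules and the barrier checklist.

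The cost is a few sentences in the plan, slightly more coding and a few more themes to report. Recruitment, sample size and power are unchanged.

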## Phase 2:

Phase 2 of the study will involve 5 Steps: 1) Web-based pre-interface survey; 2) web-based screening and tailored education and resource links; 3) post-interface satisfaction and intended care survey; 4) random assignment to concierge nurse case manager versus in place OEF/OIF/OND outreach workers 5) post-intervention follow-up.

## Phase 2: Web-based Interface & Concierge Intervention

Setting: The study will be based in Iowa City but implemented by mail and web to the RNG servicewomen in PBRN and CREATE study states in order to utilize our already established directory of resources and relationships. The concierge NCM will be based in Iowa City and perform interventions by telephone with toll free Veteran access available. There will be pre-study briefing with key VA staff (OEF/OIF/OND Outreach Counselors, Women Veteran and MST Coordinators) within each of these states. The existing infrastructure of the PBRN and CREATE relationships and resources will assist us to provide optimal subject education and access to VA care.

Participants: Participants will be delimited to RNG servicewomen returning from deployment within the 24 months preceding study participation to PBRN and CREATE study states (California, Iowa, North Carolina and Minnesota) and who have no disabilities that would interfere with their capacity to complete a web-based survey.

Sampling: Subjects will be selected through the Defense Manpower Data Center (DMDC) with which [name] has a successful working relationship. Our previous work, on which this study builds, used military e-mail as the sole method of contact. We learned several lessons: (1) RNG servicewomen only sporadically checked their military e-mails which was problematic for recruitment; (2) feedback from participants told us that e-mailing a traditional IRB study invitation and informed consent (6-7 pages) was a participation deterrent; (3) we were unable to follow up with non-responders and determine a true response rate because our original QUERI sampling specifications to DMDC did not request additional information. Consequently, we have revised our protocol for recruiting: (1) we have increased the recruitment and follow-up duration; (2) we have worked with our IRB and Pharos Innovations (developer of the web-based program) to streamline the subject information and consent process; and (3) we have thus revised our DMDC registry requirements to sample potential participants with both e-mail and postal mail. Our respondents will be contacted initially by postal mail with study materials and web-based study link and notification that an e-mail is being mailed the same week for their convenience. Non-responders will be re-contacted in 10 days following initial mailing. DMDC is able to provide sociodemographic and military information (e.g. age, marital status, race, rank, number of deployments) that will subsequently allow us to compare study participants with refusals and non-responders. This will facilitate follow up and better analysis of the generalizability of findings. Web-based interface participants will be reimbursed \$30.00 for their participation.

Sample Size: Taking into account a conservatively estimated e-mail only response rate (15%) and response rates based on letter contact and phone follow-up (48% - 70%), we conservatively estimate a 20% response rate using e-mail and letter recruitment and therefore will request a sample of 2,000 women from DMDC to achieve a final sample size of 400. Assuming conservatively that 30% of the sample will screen positively for PTSD (45% of RNG women participating in our original QUERI web-based screen met criteria for PTSD), this will allow us to have at least 120 women with a positive screen for PTSD.

Phase 2 Intervention Process: The web-based interface provides online screening scores and individually tailored educational and referral information to participants (see appendix for current version). Following IRB approval, potential subjects will receive a postal mail invitation and information summary. This will be followed within the same week by an e-mail summary of the project and invitation to complete an online tailored questionnaire that will be administered using software developed by Pharos Innovations Corporation. In the email, potential subjects will be provided with an embedded web link and a subject identification number that can be used to access the online survey/educational interface. A consent document will be included in the initial survey screens prior to beginning the survey. The survey and responses will be maintained on a secure server behind the VA firewall. The web-based pre-screening survey will query prior and current VA utilization and their reasons for accessing it or not, knowledge about post-deployment VA eligibility and services and satisfaction with VA care, a brief check list of barriers and facilitators to VA MH care and to EBP (gathered from focus group information), and non-VA MH service use.

The web-based screens will include the following:

1. PTSD - VA Post-Traumatic Stress Disorder (PTSD) Screen
2. Sexual Trauma - VA Military Sexual Trauma Screen
3. Combat Exposure - Exposures to Combat Screen (Hoge et al (2009))
4. Domestic Violence - American College of Obstetrician and Gynecologist domestic violence screen
5. Family Readjustment- developed from PI's focus groups from another HSR&D funded study
6. Substance Abuse - AUDIT-C Substance Abuse Screen (VA screen)
7. Prescription Drug Abuse- DoD Survey of Health Related Behaviors modified for web
8. TBI - VA Traumatic Brain Injury (TBI) Screen, modified to include more descriptive questions
9. Depression - Physician's Health Questionnaire (PHQ-9) depression questions

Even though the focus of this study is on PTSD, these additional screens are necessary because of frequent comorbidities with PTSD and also to inform the NCM regarding the comorbid conditions. In our preliminary study of this web-interface, most participants completed the screening and education on the same day (92%). Those who did finish the interview on the same day had an average completion time of 26 minutes (median of 17 minutes), ranging from 8 to 221 minutes.

Participants can finish the survey in one or multiple occasions. Those who sign on for more than one occasion can go directly to the last completed question. Participants who screen positive for PTSD or other mental health disorders/concerns will be given immediate web-based feedback about the domains for which they screened positively. On-line notification for those who meet screening criteria for PTSD or other conditions will include an indication to the participant of the importance of face-to-face evaluation, education about each mental health domain there is a positive screen for, and links to contact information for OEF/OIF/OND outreach personnel and VA services in their geographic region to facilitate access to care. Educational materials will include information about what PTSD or the mental health or adjustment concern is, what to expect, how commonly it occurs, treatment options, and what treatments are available in the VA. Key information about PTSD EBP will be provided. Following completion of questions and access to educational information, participants will be asked to complete the post-intervention information and satisfaction survey online. The VA Crisis Hotline toll free number available 24 hours a day will be provided.

All contact professionals and PBRN/CREATE sites will be involved prior to study initiation, educated about this study, and engaged in facilitating outreach and care. It is noteworthy that our research team's studies that use focus groups and telephone interviews with more intensive questions about sexual assault in RNG populations have not resulted in any subsequent clinical emergencies. Women who have no positive screens will be able to access the same educational information and web links if they choose to. The web-based post-screening survey immediately following the screening and education interface will be revised from our original web-and semi-structured survey to include satisfaction with information about VA MH and EBP for PTSD that they receive in the web education intervention. We will also repeat the check-list of barriers and facilitators to VA MH care and to PTSD EBP tailored from the participant's prior responses to determine if the web-based intervention altered their perceptions. We will also query those who are PTSD positive and who are not engaged in PTSD EBP and other MH care whether they intend to seek care as a result of their participation and why or why not. Participants will be reimbursed \$30.00 for the time and effort to complete the web-interface and pre-and post-surveys. If they complete the web-interface and pre and post surveys within two weeks following their initial postal or e-mail invitation then they will receive an additional \$10.00. In order to receive subject reimbursement, participants will be asked to provide their names and social security number to the coordinator through a toll-free number. These data and linkage study ID number will be maintained in a locked and limited access research network electronic file behind the VA firewall. With these subject identifiers we are able to access participant VA records, given subject IRB consent. VA health services utilization will be obtained from all consenting participants in this phase of the study, including initiation of mental health services (either in primary care or specialty care) and extent of participation in EBP. Participation will be measured by self-report of EBP engagement, type, and number of sessions. This will be validated by VA electronic chart review.

**Random Assignment to Route of VA PTSD EBP Access:** As indicated in their IRB informed consent document for study Phase 2, RNG women Veterans who screen positive for PTSD will be randomly assigned by the web interface to one of two conditions: 1) a study-specific nurse NCM using shared decision-making to assist with

local VA mental health and PTSD evaluation and treatment in the Veteran's locale, or 2) OEF/OIF/OND outreach coordinators in place at every VA. A toll-free number will be provided to participants assigned to the NCM with information that they can initiate contact and that they otherwise will be telephoned by the NCM within 2 weeks following completion of the post-intervention survey. Pharos Innovations (web-interface developer) will provide immediate notification to the study NCM of participants who are assigned to each group and she will be able to access web results of participant study screens. Upon telephone contact with the participant, the concierge NCM will engage the patient and by telephone administer a 17 item PTSD Checklist (PCL) developed by the National Center for PTSD to assess the presence of DSM-IV criteria for PTSD. She will use the PCL-S that allows identification of a specific traumatic event. This will assist with PTSD validation and allow for individualized referral. The NCM will then follow shared decision making protocols for specific domains (Joosten et al., 2008). Domains include (pending focus group augmentation): 1) Actively reporting all information and PTSD treatment possibilities to the patient/consumer. The NCM can recommend an option but PTSD treatment and therapy are decided jointly; 2) Encourages the patient to discuss preferences and form their own judgment regarding the harms and benefits of PTSD treatment/EBP options; 3) Makes sure that the information exchange is two-way between patient and NCM; 4) NCM informs partner or key family members who the Veteran includes in the telephone interface in the PTSD treatment decision-making process; 5) Informs Veteran about routes of access to VA or if already enrolled ways to access PTSD EBP and facilitates as needed and actively links with care; and 6) Addresses barriers and facilitators checked by the Veteran on her web-based interface and assists the Veteran in addressing these (e.g., education regarding night clinics, transportation). The NCM will review all PTSD treatment options, including pharmacotherapy and site specific options, e.g. unique groups. Subjects will be educated about the efficacy, risks and benefits, duration of each treatment option. Participants are welcome to re-contact the NCM on our toll free number for further questions and assistance with care initiation or transitions during the duration of the study. However, the NCM will not initiate further follow-up. The study concierge NCM, [name], R.N., M.S. will build on her own skills as a career Army nurse and prior OEF/OIF outreach counselor. She will be trained in the intervention protocol by PI ([name]) and co-I (MV) who are MH care professionals with unique clinical and research expertise specific to this intervention. NCM model fidelity and tools developed (manual, check lists for PTSD and MH utilization, satisfaction) will be guided by consultant [name], who has expertise specifically useful to this with his work with the VA's Translating Initiatives for Depression into Effective Solutions (TIDES) project in his QUERI implementation expert role. It should be noted that the NCM will use VA/DoD Clinical Practice Guidelines for The Management of PTSD (<http://www.healthquality.vagov>) for assistance with patient education, management, and tracking utilization specific to EBP but also other PTSD treatment interventions documented on the treatment checklist tracking utilization in post-intervention follow-up. Use of PBRN and CREATE study sites will allow NCM interface with PC, WHC, and MH teams already sophisticated about and engaged in evolving women's health care and research. This existing infrastructure of relationships and resources will facilitate the successful implementation and evaluation of the NCM linkage intervention. Traditional OEF/OIF/OND outreach counselors educate returning Veterans about their VA eligibility, facilitate enrollment and subsequent appointment scheduling. The NCM will have a complementary role in that her interventions will be specific to PTSD and EBP treatment.

**Post-Intervention Follow-up:** Women who screened positive for PTSD and were randomly assigned to NCM or usual OEF/OIF/OND outreach VA PTSD treatment access route will be contacted by the study research coordinator by telephone at 6 and 12 months following web-based interface. The study coordinator will use an IRB approved call contact protocol varying times of day and days of week (used successfully by this team) and ask willing participants brief questions using computer-assisted telephone interview data collection.

Satisfaction with access route and consumer feedback regarding these will be assessed. Those who did not engage in VA MH or EBP will be queried to determine if they have sought non-VA care for their PTSD, including EBP, and current factors influencing needed PTSD services. Using DMDC data, this group will be compared to VA users with regard to access and military characteristics (e.g. rank, number of deployments) in addition to web-based screening data. Women who did engage in VA MH or EBP will be asked about their experiences and satisfaction with EBP and VA care. VA service use will be validated by electronic records. Participants will be also asked about their current satisfaction with the effectiveness of the web-based interface and subsequent utilization of educational links. Non-users will be asked about current barriers to VA and MH services and again offered assistance with access to VA care and EBP if desired. We will use DMDC data to provide comparison to women who initially screened positive for PTSD. Women completing the 6 and 12 month follow-up interviews will be reimbursed \$15.00 for each completed interview.

Sample Size Analysis and Statistical Plan: The pre- and post-satisfaction surveys integrated within the Phase 2 web-based interface will be analyzed to estimate prevalence of post-deployment mental health concerns, pre-interface knowledge and current health care use, and post-interface knowledge, satisfaction, and participants' intentions to seek services for mental health care needs identified through the web-based screening.

Descriptive statistics will be used to analyze individual items and mean scores on each of the various screens. Estimated power for within group mean differences (i.e., paired t-tests) based on the smaller of the two groups (i.e., N=400: 120 PTSD positive/280 PTSD negative) and assuming a conservative variance=2 and a mean difference of .5, then power=97%. A larger sample size n=280), a smaller observed variance, or a larger observed mean difference would all provide additional power. The power to detect mean differences between groups (120 PTSD positive v. 280 PTSD negative) assuming a conservative variance=2 and a mean difference is calculated to be of .5, then power=90%. Power estimates for differences in proportions are expectedly lower but are estimated to be over 90% to detect medium effect sizes (>.4) and 54% to detect small (>.2) effect sizes. Using nQuery 4.0 for power calculation, we found we can detect a 25% difference in the proportion of women with mental health service use (which can be measured for all participants using VA databases) comparing NCM with existing outreach with 81% power using a simple test of proportions. Using logistic regression for the dependent variable of mental health service use and adjusting for covariates such as comorbid substance abuse, depression, and other post-deployment problems, we estimate that we can detect an odds ratio of 2.3 with 84% power or 2.0 with 76% power for NCM vs existing outreach. Given the appealing and personal nature of the concierge NCM, we believe we will find a large OR of these magnitudes.

OMB Considerations: Our QUERI RRP that serves as the foundation for this CREATE proposal was exempt from OMB review since the survey and collection of information being conducted was in connection with research to prevent a clinical disorder (identified as a basis for exemption under 5 CFR 1320.3). We anticipate that this will be the case with this study as it addresses prevention of chronic PTSD entrenchment and associated mental health or social issues (e.g., depression, substance abuse, marital or family maladjustment). We readily obtained OMB exemption for our HSR&D and DoD funded studies with similar domains in OEF/OIF/OND servicewomen.

Study Feasibility: We know that this study is feasible as DMDC has identified that there are currently 3,000 Reserve and National Guard (RNG) servicewomen who have returned in the past two years from deployment to Iraq or Afghanistan from the PBRN-and CREATE associated study states of California, Iowa, North Carolina and Minnesota. Of these nearly all (99.5%) have a postal address and 93% have an e-mail address.

This study is also feasible because of our successful relationship with Pharos Innovations, the corporation that assists with the web-based implementation and has a dedicated research server behind the VA Firewall. Pharos follows standards for Section 508 compliancy, therefore allowing future accommodation of Veterans with disabilities should there ultimately be a MHV interface about how to access care generally and emergently.

We plan to refer to this project with a different title during study implementation in order to make it more engaging and easy to remember. Our title "Web and Shared Decision Making for Reserve/National Guard Women's PTSD Care" will be replaced with the following working title:

